4.2.5 Potential impact of Coronavirus Disease 2019 on dropouts or missing data

The Coronavirus Disease 2019 (COVID-19) pandemic may cause disruption in the conduct of ongoing clinical trials including treatment and study withdrawals, subjects missing study visits, and/or visits being performed remotely instead of at site. Therefore, for subjects enrolled after 30 May 2020, an additional eCRF page will be foreseen. Sites will complete this page in case a subject was impacted by COVID-19 during the study. The COVID-19 Impact eCRF page will include the timing and impact of COVID-19, and relationship to COVID-19 (ie, whether the subject has confirmed/suspected COVID-19 infection, or whether the impact was related to general circumstances around COVID-19 without infection).

4.3 Interim analyses and data monitoring

No formal interim analysis is planned for this study; however, PK and safety data will be presented to and reviewed by a DMC. The DMC will oversee the PK and safety of the study by reviewing the PK and safety data periodically, in order to evaluate the risk-benefit profile in relation to the overall progress of the study. The DMC will make recommendations regarding subject safety and continuance of the study based on the observed risk-benefit of the emerging data; however, no formal statistical stopping rules will be defined.

The DMC will perform interim reviews of the PK and safety data to ensure subject safety. The first DMC meeting to review safety data will occur after the Exploratory Cohort (6 subjects) completed the study. The remaining DMC meetings will take place after completion of each of the 3 Confirmatory Cohorts (12 subjects each) but no later than in intervals of 6 months between meetings.

The DMC or Sponsor can convene an ad hoc DMC meeting to review the data and make recommendations on the continuation or modification of the study. The objectives and procedures for the DMC will be detailed in the DMC Charter. A DMC SAP will be developed and will capture analysis needed for DMC.

4.4 Multicenter studies

The results will not be presented by individual center.

4.5 Multiple comparisons/multiplicity

Not applicable for this study. The study is not statistically powered, and all analyses are of descriptive nature. No statistical tests will be performed.

4.6 Use of an efficacy subset of subjects

The efficacy analysis will be based on the FAS subjects from the Confirmatory Cohorts.

The efficacy evaluation at the end of the Down-Titration Period will be based on the subset of subjects in the Confirmatory Cohorts who enter the Down-Titration Period.

4.7 Active-control studies intended to show equivalence

Not applicable for this study.

4.8 Examination of subgroups

All efficacy variables will be analyzed by

1. Primary cause of seizure subgroups: HIE, ischemic stroke, intracranial hemorrhage, epileptic encephalopathy/genetic epilepsy, intracranial infection, brain malformation, inborn error of metabolism, undetermined causes, other.
2. Concomitant use of hypothermia subgroups: yes, no.

5 STUDY POPULATION CHARACTERISTICS

5.1 Subject disposition

The number of screen failures and the primary reason for screen failure will be summarized for all enrolled subjects (ie, all subjects with the signed informed consent).

Disposition of subjects screened will be summarized overall and by sites: the date of first subject in, date of last subject out (latest scheduled or unscheduled visit), and the number of enrolled subjects will be summarized for all study sites and by study site. Additionally, the number of subjects in each of the SS, FAS and PK-PPS will be summarized overall and by cohorts.

Disposition and Discontinuation Reasons by Periods

- Subjects started study
- Subjects entered treatment
- Subjects completed study
- Subjects discontinuing the study and primary reason for discontinuation
- Subjects started Screening Period
- Subjects completed Screening Period
- Subjects discontinuing the study during the Screening Period and primary reason for discontinuation
- Subjects started Evaluation Period
- Subjects completed Evaluation Period
- Subjects discontinuing the Evaluation Period and primary reason for discontinuation
- Subjects entering BRV Extension Period
- Subjects switching to Oral Solution prior to entering the BRV Extension Period
- Subjects completed BRV Extension Period
- Subjects qualifying to enter the Long-Term Follow-up study
- Subjects discontinuing during the BRV Extension Period and primary reason for discontinuation
- Subjects entering Safety Follow-Up Period and not entering BRV Extension Period
- Subjects entering Down-Titration Period and not entering BRV Extension Period (Confirmatory Cohorts)
- Subjects completed Down-Titration Period (Confirmatory Cohorts)
- Subjects discontinuing during the Down-Titration Period and primary reason for discontinuation (Confirmatory Cohorts)
- Subjects entering Safety Follow-Up Period after completing Down-Titration Period (Confirmatory Cohorts)

All percentages will be relative to the number of enrolled subjects.

Discontinuation due to Adverse Events

A summary of discontinuations due to AEs for the SS will present the number and percentage of subjects who discontinued this study due to AEs overall, and by type of AE.

Listings of study eligibility criteria text, of subjects who did not meet study eligibility criteria, of subject disposition and of subject analysis sets will be provided for all subjects screened.

5.2 Protocol deviations

The number and percentage of FAS subjects with no important protocol deviations and at least 1 important protocol deviation will be summarized overall, and by main category of protocol deviation (Inclusion criteria deviation, Exclusion criteria deviation, Withdrawal criteria deviation, Prohibited concomitant medication, use incorrect treatment or dose, Treatment non-compliance, Procedural non-compliance). Additionally, the number and percentage of subjects excluded from the PK-PPS due to important protocol deviations will be summarized overall and by main protocol deviation category for the FAS. Other specific categories of protocol deviations will be defined within the IPD specifications document.

Listing of subjects excluded from PK-PPS will be provided.

Listing of important protocol deviations will be provided for the SS.

All completed COVID-19 Impact eCRF pages and other IPDs will be discussed in IPD meetings, including whether the deviation may have been caused by COVID-19.

All data collected from the COVID-19 Impact eCRF page will be listed only.

6 DEMOGRAPHICS AND OTHER BASELINE CHARACTERISTICS

6.1 Demographics

Demographic summaries will be presented for the FAS, PK-PPS and SS overall and by cohorts. The variables to be considered are:

- Corrected gestational age
- Postnatal age (as defined in [Section 3.3](#))
- Gestational age (as defined in [Section 3.3](#))
- Gestational age category (Pre-term <37 weeks vs Full term \geq 37 weeks)
- Gender
- Weight (g)
- Length (cm)
- Head circumference (cm)
- Racial group (American Indian/Alaskan Native, Asian, Black, Native Hawaiian or Other Pacific Islander, White, and Other/Mixed)
- Country
- Apgar score (1 minute)

- Apgar score (5 minutes)
- HIE status

The listing of demographics including Apgar score will be provided for all subjects screened.

6.2 Medical history and concomitant diseases

The number and percentage of subjects with a medical history (if available) condition including both resolved and ongoing conditions at the time of study entry will be summarized overall and by MedDRA primary system organ class (SOC) and preferred term (PT) for the SS.

Listing of medical history glossary and medical history (if available) will be provided for the SS.

6.3 Diagnosis of epilepsy

Listing of diagnosis of epilepsy will be provided for the SS.

6.4 Prior and concomitant medications

Each medication recorded on the Prior and Concomitant Medication eCRF will be classified as either an AED or a non-AED medication based on the coded Preferred Drug Name. Medications which pharmacologically can be classified as an AED but which were taken for non-epilepsy indications may also be classified as AEDs. Identification of medications as a non-AED or AED will be done using the UCB file:

AEDs_ATCs_SEP2017_FINAL_benzo_groups_23JUL2019.xls. The classification of such medications will be confirmed prior to database lock. Listing of prior and concomitant medications indicating whether medication is AED or not will be provided for the SS. Glossary of all prior and concomitant medications indicating AED and non-AED medications will be provided for the SS.

For the summarization, similar AEDs are grouped and summarized together. For example: Valproate includes valproate sodium, valproate semisodium, valproate bismuth, valproate magnesium, valpromide, ergenyl chrono, valproic acid; Phenytoin includes phenytoin sodium, phenytoin calcium, mephenytoin, zentronal, metetoin, ethotoin, albutoin, hydantoin, phelantin, hydantol D, anirrit, dintoinal, fosphenytoin sodium, phenytoin, fosphenytoin, hydantoin derivatives, hydantoin; Phenobarbital includes phenobarbital sodium, methylphenobarbital, metharbital, alepsal, phenobarbital, kaneuron, epanal, phenobarbital calcium, phenobarbital diethylamine, phenobarbital magnesium, phenobarbital quinine. Benzodiazepine AEDs that can be grouped by Bromazepam, Alprazolam, Cloxazolam, Diazepam group, Chlordiazepoxide, Clonazepam, Cllobazam, Lorazepam, Clotiazepam, Temazepam, and Clorazepate are considered the same AED at the group level. Combination AEDs are not considered for grouping.

6.4.1 Medications at study entry

Medications with the start date and time prior or equal to the date of signed informed consent are considered medications at study entry.

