7.10 Randomization and numbering of subjects

Because N01349 is an open-label, single-arm study, subjects will not be randomized to any treatment groups. The first 6 subjects meeting the eligibility criteria will be assigned to the Exploratory Cohort. Subsequent subjects will be assigned to the Confirmatory Cohorts.

An IRT system will be used to assign eligible subjects to a treatment regimen based on a predetermined packaging schedule provided by the Sponsor. The IRT will generate individual assignments for subject kits of BRV, as appropriate, according to the cohort assignment and dosing schedule.

After the ICF has been signed and dated, the subject will be enrolled in the study. The Investigator or designee will contact the IRT and provide brief details about the subject enrolled. Each subject will be assigned a 5-digit number that serves as the subject identifier throughout the study. The IRT will allocate kit numbers to the subject based on the subject number during the course of the study. The subject number will be required in all communications between the Investigator or designee and the IRT on a particular subject. Subject numbers and kit numbers will be tracked via the IRT.

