8.2.1 Screening Period

The Screening Period will be from the signing and dating of the written ICF by the parent(s) or legal representative(s) of the subject up to initiation of the first BRV dose. Any AEs, AEDs, concomitant medications, and medical procedures will be collected after the ICF is signed. The subject's eligibility to participate in this study will be assessed. The subject identification card will be dispensed.

The Screening Period starts up to 36 hours prior to the first administration of BRV. The treatment with one or more of the following AEDs prior to or at the time of enrollment: PB, MDZ, PHT, LEV ($\leq 60\text{mg/kg/day}$), or LDC (first-line, second-line, or subsequent treatment; choice of treatment, dose, and dosing regimen at the Investigator's discretion) may have started prior to the subject's enrollment in the study and/or at a location other than the study site.

At the determination of the Investigator, subjects achieving adequate seizure control following any of the following AEDs: PB, MDZ, PHT, LEV ($\leq 60\text{mg/kg/day}$), or LDC will be considered AED responders. Those subjects will be classified as screen failures and will not be assigned to BRV treatment.

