6.4.2 Concomitant medications

Medications that were taken on at least one day in common with the study medication dosing period regardless of the start and stop date and time are defined as concomitant medications. This definition includes 1) medications with the start date and time taken after the first dose of study medication but prior to the last dose of study medication, 2) medications with the start date and

time prior to the date and time of the first dose of study medication but with the stop date and time after the first dose of study medication.

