6.4.5 AEDs taken at study entry

The number and percentage of subjects taking AEDs at the time of study entry will be summarized by WHO-DRL preferred drug name for the SS. Subject data listing for AED taken at study entry will be provided for the SS.

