6.4.6 Concomitant AEDs

The number and percentage of subjects taking concomitant AEDs will be summarized by WHO-DRL preferred drug name for the SS. Subject data listing for concomitant AED will be provided for the SS.

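### AEDs stopped before consent are tabulated as being taken at study entry, and an AED given only between consent and first BRV can miss both AED tables

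*SAP*

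**What the plan says.** SAP 6.4.1 gives the study-entry class: "Medications with the start date and time prior or equal to the date of signed informed consent are considered medications at study entry". Only the start is tested. SAP 6.4.5 turns this into a table: "The number and percentage of subjects taking AEDs at the time of study entry will be summarized", by preferred drug name, for the Safety Set.

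SAP 6.4.2 gives the concomitant class: "Medications that were taken on at least one day in common with the study medication dosing period". It adds that this holds whatever the start and stop times, then names two included cases. The second is a drug started before first BRV "but with the stop date and time after the first dose of study medication". SAP 6.4.6 tabulates this class: "The number and percentage of subjects taking concomitant AEDs will be summarized by WHO-DRL preferred drug name for the SS".

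These are the only two AED tables defined by timing. The word prior appears in the titles of SAP 6.4 and 4.2.1 but is not defined. SAP 6.4 also plans a listing: "Listing of prior and concomitant medications indicating whether medication is AED or not will be provided for the SS".

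On timing, Protocol 7.10 places enrollment at consent ("After the ICF has been signed and dated, the subject will be enrolled in the study"), and Protocol 8.2.1 allows a long interval before BRV: "The Screening Period starts up to 36 hours prior to the first administration of BRV".

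**The concern.** The trial population is defined by seizures not controlled on previous AEDs. Protocol 6.2 (exclusion 2) excludes babies who respond to the AED given immediately before BRV, and Protocol 8.2.1 makes screen failures of those controlled on a listed AED. SAP 8.2.2 compares the BRV responder rate descriptively with published second-line rates. To judge that comparison, a reader needs to know which AEDs, and how many, had failed before the first BRV dose. The baseline characteristics in SAP 6.1 do not include this, so it has to come from the two AED tables.

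Those tables have two faults. The entry table mixes drugs in use at consent with drugs already stopped, under a label that says they are being taken. And neither table is anchored to the period before first BRV, so a drug started after consent and finished before BRV may appear in neither.

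**Working it through.** No figure in the plan bears on this, so there is nothing to reproduce. The check applies the two rules to worked timings and then to assumed timings over the 36-hour window.

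**Readings.** SAP 6.4.1 compares a date and time with a date, so the consent cut can be applied by date or by clock time. SAP 6.4.2 can be applied through its general sentence (shared calendar day) or through item 2 (stopped after first BRV).

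| Case | At entry, by date | At entry, by time | Concomitant, shared day | Concomitant, item 2 |
|---|---|---|---|---|
| A. Consent 08:00, AED 09:00–10:00, BRV 14:00, same day | yes | no | yes | no |
| B. Consent 14:00, AED 18:00–20:00 same day, BRV 08:00 next day | yes | no | no | no |
| C. Consent 14:00, AED 01:00–03:00 next day, BRV 08:00 that day | no | no | yes | no |
| D. Consent 20:00 day 0, AED 02:00–10:00 day 1, BRV 08:00 day 2 (36 h) | no | no | no | no |
| E. AED stopped about 10 days before consent | yes | yes | no | no |

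Case D is in neither table under every reading. Case E is at entry under every reading. Cases A to C depend on the reading.

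**When the loss occurs if both rules are read by day.** The AED must lie wholly on a calendar day strictly between the consent day and the BRV day. Two midnights must be crossed, so the interval must exceed 24 h. Exceeding 24 h is not sufficient: consent at 08:00 with BRV at 20:00 the next day is 36 h and crosses one midnight.

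**Illustrative share lost.** Assume a uniform clock time of consent, a uniform consent-to-BRV interval L, and uniform AED start and stop within it. These are assumptions, not trial data. For the day/day reading, two midnights are crossed with probability (L − 24)/24 when L > 24, and the AED lies wholly in the middle day with probability (24/L)². With L uniform on 0 to 36 h:

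share = (1/36) ∫ from 24 to 36 of [(L − 24)/24] (24/L)² dL = (2/3)(ln 1.5 − 1/3) = (2/3)(0.4055 − 0.3333) = 0.048.

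Simulation (400,000 draws per window) gives the same value and the other readings:

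| Reading (consent / concomitant) | Window up to 36 h | Window up to 24 h |
|---|---|---|
| date / shared day | 4.8% | 0% |
| time / shared day | 24.8% | 16.6% |
| date / item 2 | 24.7% | 16.7% |
| time / item 2 | 100% | 100% |

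The denominator is AEDs given wholly between consent and first BRV. The documents do not say how many there will be.

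**Effect per baby.** With 36 Confirmatory subjects, one misclassified baby moves a percentage by 1/36 = 2.8 points; within a cohort of 12, by 1/12 = 8.3 points.

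**The case against.** The case against is strong on several points.

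- A reader might infer that any AED tried and finished between consent and BRV is lost, or that every baby whose screening crosses midnight can lose one. The documents do not support that. Read by day, SAP 6.4.1 captures an AED begun later on the consent day (cases A and B), and the shared-day rule captures one finished earlier on the BRV day (cases A and C). The wider loss arises only if consent is compared by clock time or item 2 of SAP 6.4.2 is taken as controlling.
- A reader might blame the calendar-day rule. It works the other way: it is the broader rule and rescues same-day AEDs.
- The two numbered cases in SAP 6.4.2 are introduced as included in the definition, so the better reading is that they illustrate the general sentence and do not restrict it.
- Counting stopped AEDs is useful for showing previously failed drugs, and neonatal age bounds how long ago they can have stopped (at most 27 days of postnatal age at enrollment). The fault there is the label and the mixing, not the counting.
- The entry cut matches Protocol 5.1.2, which describes subjects by AEDs received up to enrollment. Those qualifying AEDs are in the entry table; only a further AED, started and finished after consent, is at risk.
- The listing keeps every recorded AED visible per baby in a trial of about 42, and responder status (SAP 8.1.1) turns on AED changes after BRV starts.

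All of this stands and limits the size of the point. It does not remove case D or case E, and it leaves the choice of reading to the programmer.

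**Conclusion.** The point holds in a limited form. Under every reading, an AED stopped before consent is reported as being taken at study entry, and an AED confined to a calendar day between the consent day and the BRV day is in neither AED table. If both rules are read by day, the second fault needs more than 24 h and two midnights, and is uncommon (4.8% of AEDs given wholly in the interval, under the uniform assumptions). It rises to about 25% if one rule is read by clock time, and is complete if both are.

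The consequence is confined to descriptive baseline tables: the summary of AEDs that failed before BRV is incomplete and mislabelled. It would be wrong to infer that data are lost, since the listing retains them, or that any efficacy endpoint changes. This is a minor point, worth correcting because prior AED failure defines the population and bears on the comparison with second-line rates. How many babies are affected cannot be known from the documents.

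**What to change.** Add a defined class of prior AEDs: any AED started before the date and time of the first BRV dose, split into stopped before that dose and ongoing at it. Tabulate it by drug and by number per baby (1, 2, ≥3), for the Safety Set and for the Confirmatory Full Analysis Set. Either relabel the SAP 6.4.5 table as AEDs started by consent, or require that the drug was not stopped before consent.

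In SAP 6.4.2, state that the general sentence governs over its two examples. Alternatively move to date and time, but only together with the new prior class and a rule for missing times; SAP 4.2.1 imputes partial dates and gives no rule for a missing time. A move to date and time alone would widen the gap: with consent compared by date, the illustrative share in neither table rises from 4.8% to 24.7%.

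The cost is SAP wording, one extra table and the missing-time rule. The medication data are already collected, and the change should be made before database lock.

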6.4.2 Concomitant medications

Medications that were taken on at least one day in common with the study medication dosing period regardless of the start and stop date and time are defined as concomitant medications. This definition includes 1) medications with the start date and time taken after the first dose of study medication but prior to the last dose of study medication, 2) medications with the start date and

time prior to the date and time of the first dose of study medication but with the stop date and time after the first dose of study medication.

6.4.3 Non-AEDs taken at study entry

The number and percentage of subjects taking non-AED medications at the time of study entry will be summarized overall and by WHO-DRL pharmacological group (Anatomical Therapeutic Chemical [ATC] classification level 1), therapeutic subgroup (ATC classification level 2) and preferred drug name for the SS. Subject data listing for non-AED taken at study entry will be provided for the SS.

6.4.4 Concomitant Non-AEDs

The number and percentage of subjects taking concomitant non-AEDs will be summarized similar to non-AEDs at study entry for the SS. Subject data listing for concomitant non-AED will be provided for the SS.

6.4.5 AEDs taken at study entry

The number and percentage of subjects taking AEDs at the time of study entry will be summarized by WHO-DRL preferred drug name for the SS. Subject data listing for AED taken at study entry will be provided for the SS.

6.4.6 Concomitant AEDs

The number and percentage of subjects taking concomitant AEDs will be summarized by WHO-DRL preferred drug name for the SS. Subject data listing for concomitant AED will be provided for the SS.

6.5 Procedure history

Listing of procedure history will be provided for the SS.

6.6 Concomitant medical procedures

Listing of concomitant medical procedures will be provided for the SS.

6.7 Primary cause of seizure

Primary cause of seizure will be summarized by cohorts for SS. The summary analysis of the primary cause of seizure should be based on the latest data collected per subject prior to study completion/termination. Listing of all primary causes of seizure will be provided for the SS.

